7.3. Premature Withdrawal and Missing Data

All subjects who withdraw prematurely from the study/study drug will be documented and the reason for their withdrawal recorded in the final Clinical Pharmacology Study Report (CPSR). All available data from subjects who withdraw will be listed and all available planned data will be included in the summaries according to the populations defined in Section 5.

In the event that the study is prematurely discontinued, all available data will be listed and a review carried out by the study team to assess which statistical analyses are still considered appropriate.

7.4. Baseline Definition

The following table indicates the baseline day to be used in any change from baseline listings / summaries / graphical presentations or as a covariate in a statistical analysis:

Parameter	Baseline Days Collected			Baseline To Be Used in Analysis / Summaries
	Screening	Day -1	Day 1 Predose	
Safety:				
ECG	X	X		Day -1
Vital Signs	X	X		Day -1
Lab	X	X		Day -1
EPO, Hpecidin			X	Day 1 Predose

7.5. Derived and Transformed Data

7.5.1. Demographic and Population parameters

7.5.1.1. Study Day

Study day will be calculated as number of days from baseline date, as outlined below:

Scenario	Study Day
reference date is missing	study day = missing
reference date < IP start date	study day = reference date – IP start date
reference date ≥ IP start date	study day = reference date – (IP start date + 1)

7.5.1.2. Date of Birth

Note that only the year of birth has been captured, so all dates of birth are 30th June XXXX, where XXXX is the year of birth.

7.5.1.3. Age

Age is calculated based on screening date, using date of birth, truncated to integer value. Note that only the year of birth has been collected where the day and month would be 30th June for all patients. Therefore, the derivation of age will be approximate.

The derivation of age will be footnoted on appropriate displays.

7.5.1.4. Body Mass Index (BMI)

Body Mass Index (BMI) is calculated as follows:

$$\text{BMI} = \text{weight in kg} / (\text{height in cm})^2$$

7.5.1.5. Exposure

Exposure is calculated as follows:

$$\text{Study Drug Exposure (days)} = (\text{Treatment Stop Date} - \text{Treatment Start Date}) + 1$$

7.5.2. Safety Parameters**7.5.2.1. Adverse Events**

Note that the database has been designed such that AE Onset date is missing, unknown or complete; a partial/incomplete AE onset date will be considered as missing.

AE

AE Onset Time since First Dose	= AE Onset Date – Treatment Start Date (if treatment start date > AE onset date) = AE Onset Date – Treatment Start Date + 1 (if treatment start date <= AE onset date) = missing otherwise
AE Duration (in days)	= AE Resolution Date – AE Onset Date + 1
AE is “On Treatment”	if the AE onset date is on or after the treatment start date and on or before the treatment stop date
AE is “Post-Treatment”	if the AE onset date is after the treatment stop date
AE is considered drug-related	if the relationship is marked ‘Yes’ on the case report form, or the value is missing

7.5.3. Change from Baseline

The change from baseline will be calculated by subtracting the baseline values from the individual post-randomisation values. If either the baseline or post-randomisation value is missing, the change from baseline is set to missing as well.

7.5.4. Pharmacokinetic Parameters

For the purposes of calculating summary statistics and for statistical analysis, all PK parameters with the exception of tmax will be log_e transformed.

Between subject coefficient of variation CV_b (%) will be calculated according to the following methods:

Untransformed Data : $100 * (SD/Mean)$ where SD is the standard deviation of the untransformed data

Transformed Data : $SQRT(\exp(SD^2-1)) * 100$ where SD is the standard deviation of the log_e-transformed data.

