## **9.2. Sample Size Considerations**

### **9.2.1. Sample Size Assumptions**

As this study is descriptive in nature and no formal statistical comparisons of PK data will be performed, the sample size of 24 subjects (12 in each cohort) will be recruited such that at least 8 subjects complete the trial. Based on PK parameter CV% of ~50% in subjects with renal impairment or ESRD [refer to GlaxoSmithKline Document Number [RM2008/00267/07](#), 14-Oct-2015.GSK1278863 IB and associated IB supplements for GSK1278863 [GlaxoSmithKline Document Number [2015N266524\\_00](#), 17-Dec-2015; GlaxoSmithKline Document Number [2015N266524\\_01](#), 08-Apr-2016]] for a sample size of at least 8 statistically evaluable subjects, the half width of the 90% confidence interval will be within 56% of the point estimate.

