##### **9.3.2.1. Final Analyses**

Descriptive statistics (n, arithmetic mean and associated 95% confidence interval (CI), standard deviation, minimum, median, maximum) will be calculated for all pharmacokinetic endpoints of GSK1278863 and metabolites separately by cohort and overall (CAPD, APD, and both combined)

In addition, geometric means, associated 95% CIs, and estimates of between-subject CVs (CVb(%)) will be calculated for AUC (0- $\tau$ ), AUC (0- $\infty$ ), Cmax, clearance, and t1/2 where

$$\text{Geometric mean} = \exp(\text{mean on } \log_e \text{ scale})$$

$$\text{CVb}(\%) = \text{SQRT}(\exp(\text{SD}^2 - 1)) * 100, \text{ where SD is the standard deviation of the } \log_e\text{-transformed data.}$$

Similar descriptive summaries will be created for the steady-state GSK1278863 and metabolite unbound concentration and free fraction, erythropoietin, and hepcidin plasma concentration.

At a minimum, descriptive statistics (n, mean and associated 95% CI, standard deviation, minimum, median, maximum) will be calculated at each relevant time point.

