10.3. Statistical Analyses

Descriptive statistics (n, arithmetic mean and associated 95% confidence interval, standard deviation, minimum, median, maximum) will be calculated for all pharmacokinetic endpoints of GSK1278863 and metabolites by Cohort. In addition geometric means, associated 90% CIs, and estimates of between-subject CVs (CVb (%)), will be calculated for each Cohort where

Geometric mean = $\exp(\text{mean on } \log_e \text{ scale})$

CVb (%) = $\text{SQRT}(\exp(\text{SD}^2) - 1) \times 100$, where SD is the standard deviation of the \log_e -transformed data.

Steady State Assessment

Trough concentration (C_{τ}) samples collected on the specified days (Days 12, 13, 14, and the 24 h post-dose sample on Day 14) will be used to assess attainment of steady state. Individual trough concentration data C_{τ} will be plotted and listed. C_{τ} will be summarized by day and cohort, and the mean and median plots will be provided.

Steady state will be assessed separately for GSK1278863 and metabolites in each cohort.

A linear mixed effects ANOVA model will be used to evaluate steady state for GSK1278863 and each metabolite. The dependent variable will be log-transformed Predose (trough) concentrations (C_{τ}) on Days 12 to 15. Independent variables in the model include day (as a continuous variable) as a fixed effect and subject as a random effect.

Assessment of plasma GSK1278863 and metabolites steady state will be assessed by evaluating the estimated slope for the day parameter and associated 90% CI for both the cohorts combined. A steady state attainment is defined as the 90% confidence interval of the slope including 0.

Secondary Comparisons:

Assessment of Accumulation

To estimate the extent of accumulation for GSK1278863 and metabolites after repeat dosing, the observed accumulation ratio R_0 will be determined.

$$R_0 = \frac{AUC(0-\tau)_{ss}}{AUC(0-\tau)}$$

Where $AUC(0-\tau)_{ss}$ is AUC from time zero to t h under steady state and $AUC(0-\tau)$ is AUC from time zero to dosing interval at Day 1.

To evaluate the accumulation ratio, statistical analysis of GSK1278863 and metabolite PK data for each cohort will be performed separately after a log transformation of the data.

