14.1.1. Study Population

Table No.	Population	IDSL No. / Example Shell	Title	Additional Programming Notes	Responsibility	Deliverable Priority
9.1	All Subjects	ES1a	Summary of Subject Disposition	By Cohorts and both combined	QSI (Prog)	SAC
9.2	All Subjects	DM1	Summary of Demographic Characteristics	1. By Cohorts and both combined 2.Add BMI, Weight ,Height,	QSI (Prog)	SAC
9.3	All Subjects	DM5	Summary of Race and Racial Combinations	By Cohorts and both combined	QSI (Prog)	SAC
9.4	All Subjects	DM6	Summary of Race and Racial Combinations Details	By Cohorts and both combined	QSI (Prog)	SAC
9.5	Enrolled	NS1	Summary of Number of Subjects by Country and Site ID	By Cohorts and both combined	QSI (Prog)	SAC
9.6	Enrolled	DM11	Summary of Age Ranges	By Cohorts and both combined	QSI (Prog)	SAC

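### The log-scale CVb formula in protocol 9.3.2.1 and SAP 7.5.4 is mis-bracketed and contradicts SAP 10.3; the SAP's study day and BMI formulas are also wrong as written

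*SAP*

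**What the plan says.** **CVb.** Three places define the between-subject CV on the log scale, with SD the standard deviation of the log-transformed data.

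- Protocol 9.3.2.1: "SQRT}(\exp(\text{SD}^2 - 1)) * 100"
- SAP 7.5.4: "Transformed Data : $SQRT(\exp(SD^2-1)) * 100$ where SD is the standard deviation of the log_e-transformed data"
- SAP 10.3: "SQRT}(\exp(\text{SD}^2) - 1) \times 100"

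The first two subtract 1 inside the exponent and the third subtracts it outside. SAP 10.2 asks for a coefficient of variation without giving a formula, and separately asks for the SD of the log-transformed data. The protocol plans CVb for AUC, Cmax, clearance and half-life. Its sample size section works from "Based on PK parameter CV% of ~50% in subjects with renal impairment or ESRD".

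**Study day.** On or after the first dose, SAP 7.5.1.1 sets "study day = reference date – (IP start date + 1", with the bracket closing after the 1. Before the first dose it uses the plain date difference. For AE onset on or after treatment start, SAP 7.5.2.1 uses "AE Onset Date – Treatment Start Date + 1". The exposure formula in SAP 7.5.1.5 also adds 1 after subtracting.

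**BMI.** SAP 7.5.1.4 gives "weight in kg} / (\text{height in cm})^2". The programming note for demographic Table 9.2 reads "Add BMI, Weight ,Height", and ICH Listing 1 carries a matching note.

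**Amount in dialysate.** SAP 10.2 multiplies total dialysate volume by a single dialysate concentration. Protocol 6.4.2 records a volume and takes an aliquot for each drained dwell on Day 14.

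**The concern.** One statistic has two definitions, and the plan does not say which governs. The form that appears twice cannot be a coefficient of variation, because it does not go to zero when the data do not vary. No hypothesis is tested in this study, so descriptive summaries are its main output. A programmer who follows SAP 7.5.4 literally would report a variability figure that does not describe the data and cannot be set against the planning value.

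The study day rule puts the added 1 inside the subtracted bracket. That reverses its sign and gives two different dates the same number. The BMI formula mixes units.

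The dialysate amount is a request for clarification, not an error. The product is exact for one mixed bag, for equal bag volumes, or for a volume-weighted concentration. The protocol's wording on the total amount over 24 h (9.3.2.3.2) and the SAP's reference to amounts (10.1) point to a sum over bags, but no text says so. Peritoneal dialysis clearance is a secondary endpoint, so a stated rule would remove a programmer's choice.

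**Working it through.** **Which CVb form fits the plan's own figure.** Protocol 9.2.1 states a 90% CI half-width within 56% for n = 8 and CV ~50%. Inverting the SAP 10.3 form:

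- SD = sqrt(ln(1 + 0.5²)) = sqrt(ln 1.25) = 0.4724
- Half-width = exp(t × SD × sqrt(k/n)) − 1, with t(0.95, 7 df) = 1.8946
- k = 2 (paired ratio such as Day 14 to Day 1): exp(1.8946 × 0.4724 × sqrt(2/8)) − 1 = 56.4%, which matches
- k = 1 (single geometric mean): 37.2%
- SD set equal to CV instead: 60.6% (k = 2) or 39.8% (k = 1)

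Of the variants tried, only the standard conversion reproduced 56%, and it needs the paired-ratio variance, which the protocol does not state. This supports SAP 10.3 as the intended form.

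**What the mis-bracketed form returns.** With SD² = ln(1 + CV²):

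100 × sqrt(exp(SD² − 1)) = 100 × sqrt((1 + CV²)/e)

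| True CV | Standard form (SAP 10.3) | As bracketed (protocol 9.3.2.1, SAP 7.5.4) |
|---|---|---|
| 0% | 0% | sqrt(1/e) = 60.65% |
| 20% | 20% | sqrt(1.04/e) = 61.9% |
| 30% | 30% | sqrt(1.09/e) = 63.3% |
| 50% | 50% | sqrt(1.25/e) = 67.8% |
| 75% | 75% | 75.8% |
| 100% | 100% | sqrt(2/e) = 85.8% |
| 150% | 150% | 109.3% |

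The two forms agree where (1 + c²)/e = c², so c = 1/sqrt(e − 1) = 76.3%. Below that the bracketed form overstates; above it, it understates. To return 50% it would need SD² = 1 + ln(0.25) = −0.386, which is impossible.

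**Study day.** Let k be the number of days from the first dose date. For k ≥ 0 the written rule gives k − 1; the AE onset rule gives k + 1.

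| Date | k | SAP 7.5.1.1 | SAP 7.5.2.1 |
|---|---|---|---|
| Day before first dose | −1 | −1 | −1 |
| First dosing day | 0 | −1 | 1 |
| Second dosing day | 1 | 0 | 2 |
| 14th dosing day | 13 | 12 | 14 |

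The AE rule agrees with the Day 1 and Day 14 labels in protocol 3.1. The study day rule does not.

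**BMI.** Heights are not in the documents, so these are assumed. At 70 kg and 170 cm: 70/170² = 0.0024 as written, against 70/1.70² = 24.2. At the protocol's weight limits, with assumed heights: 45 kg and 150 cm gives 0.0020 against 20.0; 140 kg and 190 cm gives 0.0039 against 38.8. The factor is always 100² = 10,000.

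**Dialysate amount.** No size is computed. It depends on bag volumes and concentrations that the documents do not give.

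**The case against.** The algebra is not in dispute; the case against is about weight.

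- The correct CVb formula already stands in the SAP section on statistical analyses, and nothing shows that the other one will be programmed. True, but the protocol and the SAP's own derivation section carry the wrong form, and no text ranks them.
- No comparison of the observed CV with the planning 50% is planned, and sample size re-estimation is ruled out in protocol 9.2.3. This stands. The formula's failure at 50% shows that it is wrong; no planned decision depends on it.
- SAP 7.5.4 also gives a correct untransformed CV, and the coefficient of variation requested in SAP 10.2 may be that one. Possible, but the text does not say, and CVb on the log scale is named in both protocol 9.3.2.1 and SAP 10.3.
- SAP 8 reports 5 completers. At n = 5 and a true CV of 50%, assuming log-normal data, the 95% interval for the CV runs from about 29% to 231%, so the estimate is weak in any case. This does not excuse a systematic error in the formula.
- No display title names study day, summaries use planned times, and a constant shift over Days 12 to 15 would leave the steady-state slope unchanged. All correct. What remains is one number for two dates and two rules that disagree.
- A BMI near 0.002 would be noticed at once. Probably, and it enters no analysis.
- The CVb bracketing could be a slip in the PDF text. This cannot be fully excluded, but the same form appears in two separate documents while SAP 10.3 reads correctly. A look at the source settles it.

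**Conclusion.** The concern holds. Three formulas are wrong as written: CVb in protocol 9.3.2.1 and SAP 7.5.4, study day in SAP 7.5.1.1, and BMI in SAP 7.5.1.4. The CVb form also contradicts SAP 10.3. Programmed literally, CVb would be overstated for any true CV below 76.3%, by 17.8 percentage points at 50% (67.8 − 50), and understated above it. The table assumes log-normal parameters; the 60.65% floor needs no assumption.

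The reach is limited. Geometric means, Day 14 to Day 1 ratios and all confidence intervals are unaffected, CVb can be recovered from the reported log-scale SD, and neither BMI nor study day feeds a statistical analysis. These are corrections that should be made because the SAP is the programming specification; they do not threaten the primary estimates. The dialysate amount is a clarification only.

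**What to change.** - **CVb:** in protocol 9.3.2.1 and SAP 7.5.4 write CVb(%) = 100 × sqrt(exp(SD²) − 1), as SAP 10.3 already does. If the protocol is not amended, add a sentence to the SAP that this form replaces the one in protocol 9.3.2.1.
- **Study day (SAP 7.5.1.1):** on or after first dose, take reference date minus IP start date, then add 1. The first dose becomes Day 1 and the 14th Day 14.
- **BMI (SAP 7.5.1.4):** divide weight in kg by the square of height in metres.
- **Dialysate amount (SAP 10.2, clarification):** state Ae(0-τ) as the sum over drained bags of each bag's volume times its concentration.

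The cost is one-line text changes in five places: four in the SAP and one in the protocol, or a superseding sentence in the SAP in place of the protocol change. No new data or analyses are needed.

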7.5.5. Multiple Measurements at One Timepoint

Where multiple measurements are recorded for a particular time point, the mean of the measurements will be calculated and used in any derivation of summary statistics. However, all available data will be listed.

Where more than the specified number of measurements has been taken, the most recently recorded values will be used in the derivation of the appropriate summary measure (i.e. mean or maximum).

7.6. Values of Potential Clinical Importance

The following tables display the ranges to be used for flagging values of potential clinical importance for various parameters. These values will be flagged on the listings.

Laboratory Values of Potential Clinical Importance (Renal Failure)

7.6.1. Laboratory Values

Laboratory Parameter	Units	Clinical Concern Range	
		Low Flag	High Flag
Albumin	g/L	< 30 g/L	>55 g/L
Aspartate Aminotransferase	IU/L		≥3x ULRR
Alanine Aminotransferase	IU/L		≥3x ULRR
Bilirubin (total and direct/indirect)	μmol/L		≥2x ULRR
Calcium	mmol/L	> 0.5 mmol/L below LLRR	> 0.25 mmol/L above ULRR
Glucose, fasting	mmol/L	<3.9	>22
Sodium	mmol/L	<130	>150

Laboratory Parameter	Units	Clinical Concern Range	
		Low Flag	High Flag
Total CO2	mmol/L	<20	>32
GGT	IU/L		>=2ULRR
Alkaline phosphatase	IU/L		>=3xULRR
Uric Acid	Mg/dL		>6.0 mg/dL
Total Protein	IU/L	<LLRR	>15 g/L bove ULRR
Potassium (serum)	mmol/L	> 0.5 mmol/L below LLRR	> 1.0 mmol/L above ULRR

Laboratory Parameter	Units	Clinical Concern Range	
		Low Flag (< x)	High Flag (>x)
Hemoglobin	g/dL	< 7.5	>=13.0
Platelet Count	GI/L	< 80x GI/L	> 500x GI/L
WBC Count	GI/L	> 1x GI/L below LLRR	>5x GI/L above ULRR
Neutrophils	GI/L	< 0.5x LLRR	
Lymphocytes	GI/L	< 0.5x LLRR	

Laboratory Parameter	Units	Clinical Concern Range	
		Low Flag (< x)	High Flag (>x)
Ferritin	ng/mL		> 1200
TSAT	%	<15	>40

7.6.2. Vital Signs

Vital Sign Parameter (Absolute)	Units	Clinical Concern Range	
		Lower	Upper
Systolic Blood Pressure	mmHg	≤85	≥180
Diastolic Blood Pressure	mmHg	≤45	≥110
Heart Rate	bpm	≤40	≥110
Notes:			

 At visits where BP and HR are assessed in triplicate, the average of the 3 values will be used to assess PCI criteria. For subjects who undergo in-clinic dialysis, the post-dialysis BP and HR values will be used to assess PCI criteria, unless otherwise specified. 			

7.6.3. ECG

ECG Parameter	Units	Clinical Concern Range	
		Lower	Upper
Absolute QTc interval	msec		>480 if with bundle branch block
Change from Baseline			
QTcB or QTcF	msec		>60 msec

8. STUDY POPULATION

It was initially expected that 30 subjects (15 in each cohort) would be needed to be recruited in order to ensure that at least 12 subjects (6 in each cohort) completed the trial. However, during the informal review of the available PK data it was determined that there were no clinically-significant differences in PK between the CAPD/APD and CKD populations, therefore the planned number of subjects was reduced to enrol 7 subjects and 5 subjects completed the study in order to minimize unnecessary additional subject exposure.

Study population data will be summarised by, or under the direct auspices of, Clinical Statistics, GlaxoSmithKline.

The precise format and content of Study Population tables and listings are shown in Section 14.1.1 and Section 14.1.5 of the RAP.

The tables will use the “All Subjects” population unless otherwise specified.

8.1. Subject Disposition and Demographics

A listing of subject withdrawals will include all subjects who prematurely discontinued from the study. This listing will include the discontinuation information for each subject, if there are any, including dates of discontinuation and reason for premature discontinuation. The number of subjects who completed, withdrew, and reasons for withdrawal will be tabulated.

A listing indicating whether a subject was included in each of the analysis populations will be prepared. The number of subjects included in each analysis population will be tabulated.

Demographic and racial data will be summarized using the “All Subjects” population.

8.2. Protocol Deviations

As outlined in the protocol deviation plan the protocol deviations will be discussed and reviewed by the study team. The frequency of the review may be amended dependent on the outcome of the initial reviews. Any protocol deviations identified will be entered into InForm eCRF. Prior to each review the DQL will run the protocol deviation check log and protocol deviation log report in InForm, discrepancies will be resolved and the report issued to the reviewing study team.

All protocol deviations that are data based will be listed.

8.3. Concomitant Medications

All medications will be coded using the GSK Drug dictionary. Medications will be classified into preferred term and body system, using the GSK-Drug Anatomical Therapeutic Clinical (ATC) classification. ATC level 1 (the body system) will be shown. Medications will be sorted in descending order of total incidence across treatment groups for the ATC level 1 and in descending order of total incidence for the preferred term within each ATC level.

Medications will be defined as follows, where it should be noted that a medication can be counted in more than one phase:

Prior	- any medication taken up to, but not including, the start date of study medication (pre-treatment phase). Therefore, prior medications have stopped prior to the subject taking study medication.
Concomitant	
 - if a medication is started or stopped on the same day of taking the first or last dose of randomised investigational product then this will be considered a concomitant medication (on-treatment phase) - any medication started before last day in the study and the drug stop date is either missing or on or after treatment start date - any medication with start date missing yet the stop date is on or after treatment start date - if both start and stop dates are missing the drug is specifically indicated as continuing in the trial.
Post study	- any drug with start date on or after last day in the study will be considered post-study drug. This will not be summarized with concomitant drugs but will be included in data listing.

In situations where the concomitant medication status of the drug cannot be determined, available relevant information will be reviewed on a case-by-case basis to determine the status whether it should be considered ‘concomitant’ or ‘post-study’ by Clinical; the decision of the clinical group will be considered final. However, if such determination cannot be made unambiguously, the medication will be considered concomitant.

Concurrent medications will be listed, and summarized by generic term, if more than 20 concomitant medications were used.

9. SAFETY ANALYSES

Safety data will be summarised and listed by, or under the direct auspices of Clinical Statistics, GlaxoSmithKline.

The precise format and content of Safety tables, ICH and Other listings are shown in Section 14.1.2, Section 14.1.5 and Section 14.1.6 of the RAP.

The tables will use the “All Subjects” population unless otherwise specified.

